10.2. Trial design

Sample size for the trial is based on a primary endpoint of quality of the radiation dose distribution. As described above, the GammaPod dose will be scored as acceptable, acceptable but with a minor deviation, or unacceptable using the criteria described in Section 5.5.4. All eligible patients will be included in the analysis. If a treatment plan is graded as unacceptable, the treatment will be aborted and the GammaPod boost will not be delivered. The patient will in that case be treated with a conventional boost following whole breast radiation (i.e. 16 Gy in 8 fractions using electrons or photons with conventional linear accelerator). The optimal two-stage trial design by Simon will be used(47). This tests the null hypothesis that, for a population of patients, the true proportion of patients for whom the GammaPod treatment planning system is able to generate an acceptable dose distribution is less than or equal to 60% (a chosen value signifying that the device has significant clinical utility if the null hypothesis is false). Given only a limited sample size in the study, the proportion of patients in the study for whom treatment plans must be acceptable for the null hypothesis to be found false (to a low uncertainty) must in fact be considerably higher than 60% (see below). Specifically, the number of acceptable plans and the total number of plans must be such that there is a certain low probability (chosen here as less than 5%) that the device will be found acceptable in the trial when in fact it would be acceptable for less than 60% of patients in a very large population of patients. That is, there is only a 5% chance that the device will be found to have significant utility when in fact it does not. In the design, there is also an alternative hypothesis that the true proportion of patients with an acceptable dose distribution is greater than or equal to 90%. Again, the required total number of patients in the study and the number for whom plans are acceptable must be sufficient for there to be a certain low probability (chosen as less than 10%) that the null hypothesis is found to be true when in fact the alternative hypothesis is true. That is, there is only a 10% chance that the device will be found to not have significant utility when in fact it has high utility. Furthermore, the Simon Two Stage design allows for the trial to be aborted if after plans have been generated for a subset of the total number of patients (stage 1) the number of acceptable plans is below a certain number. Using tables for Simon Two Stage design, an appropriate design has been determined to be the following:

After evaluating the device on 8 patients in the first stage, the trial will be terminated and the device rejected if the dose distribution is acceptable for only 5 or less patients. If the trial goes on to the second stage, a total of 17 patients will be studied. If the total number of patients for whom the dose distribution is acceptable is less than or equal to 13 the device will be rejected. If the null hypothesis is in fact true, there is a 4.4% probability of falsely concluding that it is false (the target for this value was 5% in designing the trial). This is the probability of falsely concluding that the true proportion of patients with an acceptable dose distribution is greater than 60% when in fact it is less than or equal to 60%. On the other

hand, if the alternative hypothesis is true, there is a 9.5% probability of falsely concluding that the null hypothesis is true (the target for this value was 10%). This is the probability of falsely concluding that the proportion of patients with an acceptable dose distribution is less than or equal to 60% when in fact the true proportion is at least 90%. This scheme gives a power of 90.5% (1–9.5%: the probability of concluding correctly that the null hypothesis is false when the alternative hypothesis is true). The probability of early termination after stage 1 if the null hypothesis is true is equal to 68% (early termination occurs if 5 or fewer patients are acceptable after stage 1) and the expected sample size for this trial is 10.8 accounting for the probability of early termination.

11. Potential Risks/Discomfort

GammaPod is a new radiation treatment device that has not been used on patients before. Although there has been extensive pre-clinical testing with phantoms, it is still possible that the GammaPod treatment deviates from the intended in geometry and dosimetry. Patients may not be able to tolerate the breast immobilization cups due to the negative pressure and the duration of treatment in the prone position.

To minimize the dosimetric discrepancy, the physicist co-investigator must perform a hand calculation to verify the treatment time is within 5% to the treatment time calculated by the treatment planning system before the treatment can be started. The total treatment time is a function of the target volume, the prescribed dose and the dose rate.

$$t \approx PTV \cdot D_p / \dot{D} \cdot V_f$$

where t is beam on time, PTV is the planning target volume, D_p is the prescription dose to the PTV , \dot{D} is the dose rate on the day of treatment, and V_f is the focal spot volume at the 50% isodose surface.

The maximum dose to lung and heart should be less than 2.5Gy. This limit is slightly less than the single fraction dose given in hypofractionated whole breast irradiation (2.66 Gy in Ontario trial(16), and 3.3Gy in UK START trial(18)).

To minimize the geometric error, the tumor location relative to the breast cup will be displayed on the treatment control console after the plan is transferred to the treatment control console. The envelope containing all movements of the radiation focal point of the GammaPod during the entire treatment will also be displayed against the target. The envelope of the focal spots should generally conform to the target volume and a visual verification must be confirmed before the treatment can be started.

The primary goal of the study is to assess the feasibility of using GammaPod to deliver high doses of focal radiation to the target in human breast. Patient tolerance to the breast cup and adhesive during radiation treatment, and to the prone setup, is part of the evaluation. Because we have evaluated the breast cup and prone setup in an earlier study and all subjects tolerated it well, the likelihood of intolerable discomfort or irritation is very small. Nevertheless, if 2 of the first 5 patients or more than 1/3 of the subjects thereafter complain about either the breast cup or the prone treatment setup, the study will be suspended until patient comfort is further improved.

12. Potential Benefits

The characteristics of the GammaPod dose delivery allow the GammaPod to deliver a focal radiation dose with a fast dose fall-off away from the target. It is this ability of lower dose spillage to the normal breast tissue and surrounding organs such as the lung and the heart that makes it possible to deliver an equivalent biological dose to the tumor bed in a single treatment as the conventional boost treatment that takes 8 treatments to complete. Therefore, the direct benefit to the subjects enrolled in the study is the shortening of the treatment duration by one and 1/2 week. If such dose delivery is proven feasible, the implications on the management of early-stage breast cancer are far more important. Currently in the US, more than 90% of the breast cancer patients who choose breast conservation therapy receive 33 radiation treatments that last 7 weeks. Such a protracted regimen significantly worsens the quality of life for these patients and increases health care costs.

13. Cost/Payments

The radiation treatment delivery using the GammaPod is considered experimental. The Department of Radiation Oncology will not charge the patient or her insurance company for the associated costs. The participant and/or their health plan/insurance company will need to pay for some or all of the costs of treating the cancer in this study.

The whole breast radiation therapy subsequent to the GammaPod single fraction tumor bed boost is not experimental but standard of care. The hospital will bill the patient/payer as with conventional radiation therapy.

No payment will be given to the patients for participating in this feasibility study.

14. References and GammaPod Bibliography

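### Section 10.2 acts on its rejection rule only at 8 and 17 patients, although rejection is already certain at the third unacceptable plan among the first 8 or the fourth overall

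*Combined protocol and SAP*

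**What the plan says.** Section 10.2 adopts Simon's optimal two-stage design. Under the null, the proportion of patients for whom the planning system "is able to generate an acceptable dose distribution is less than or equal to 60" per cent; under the alternative, "the true proportion of patients with an acceptable dose distribution is greater than or equal to 90" per cent.

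Decisions are placed at two counts. In stage 1, "After evaluating the device on 8 patients in the first stage, the trial will be terminated and the device rejected"; the trigger is 5 or fewer acceptable plans. After that, "If the trial goes on to the second stage, a total of 17 patients will be studied", and if the total number acceptable "is less than or equal to 13 the device will be rejected". The section reports a type I error of 4.4%, power of 90.5%, a 68% chance of early termination under the null and an expected sample size of 10.8.

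The second CT and the boost take place on one day (section 5.1). The plan must be approved before it is sent for delivery (section 1.3). A plan graded unacceptable means no GammaPod boost for that patient (sections 5.4.3 and 10.2). The only other rule based on a count of patients is in section 11: it suspends the study for comfort complaints and is unrelated to plan quality.

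**The concern.** The boundaries tolerate at most 2 unacceptable plans in the first 8 patients and at most 3 in all 17. Once a third occurs within the first 8, or a fourth overall, no later result can rescue the device under the rule. The grade is known the same day, so the investigators would know this at once. The text provides no stop at that point, and its fixed counts are the only accrual instruction given.

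Section 11 says that "GammaPod is a new radiation treatment device that has not been used on patients before". Women enrolled after rejection is certain would be fitted with the cup and have a second CT, and those whose own plans pass would receive the boost on a device that the trial is already bound to reject. The accept/reject decision would not change.

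**Working it through.** **Inputs (section 10.2).** Stage 1 size 8, reject at 5 or fewer acceptable; total 17, reject at 13 or fewer; p = 0.60 under the null and 0.90 under the alternative. Write q = 1 − p.

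**1. The plan's own figures.**
- Going on to stage 2 at p = 0.60 needs 6, 7 or 8 acceptable of 8: 0.2090 + 0.0896 + 0.0168 = 0.3154. Early termination is 1 − 0.3154 = 0.6846 (stated 68%).
- Expected sample size = 8 + 9 × 0.3154 = 10.84 (stated 10.8).
- P(accept) = Σ over x = 6 to 8 of P(Bin(8, p) = x) × P(Bin(9, p) ≥ 14 − x). At p = 0.60: 0.2090 × 0.0705 + 0.0896 × 0.2318 + 0.0168 × 0.4826 = 0.0436. The plan states: "there is a 4.4% probability of falsely concluding that it is false".
- The same sum at p = 0.90 gives 0.9045 (stated 90.5%).

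All four figures reproduce. A search over designs up to 26 patients confirms 5/8, 13/17 as the optimal design for these hypotheses and error limits.

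**2. When rejection becomes certain.**
- In stage 1, at the third unacceptable plan (8 − 5 = 3). The earliest is patient 3, leaving 8 − 3 = 5 more to fill the stage.
- In a trial that reached stage 2, at the fourth (17 − 13 = 4). The earliest is patient 10 (two failures in the first 8, then patients 9 and 10), leaving 17 − 10 = 7 more. A third failure that falls in stage 2 is not decisive.

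**3. Chance that rejection is certain before the stage is full.**
- Stage 1, at patient k = 3 to 7: C(k − 1, 2) q³ p^(k−3). At p = 0.60: 0.0640, 0.1152, 0.1382, 0.1382, 0.1244; sum 0.5801.
- Stage 2, at patient k = 10 to 16: [C(k − 1, 3) − C(8, 3)] q⁴ p^(k−4). The subtraction removes paths that already had three failures in the first 8. At p = 0.60: 0.0334, 0.0459, 0.0469, 0.0423, 0.0356, 0.0286, 0.0222; sum 0.2549.
- Total 0.5801 + 0.2549 = 0.8350. When it happens, the mean number of further patients is 2.70 / 0.835 = 3.2.

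**4. Expected saving from stopping there.** Weight each probability by the patients left to fill the stage. At p = 0.60:
- Stage 1: 5(0.0640) + 4(0.1152) + 3(0.1382) + 2(0.1382) + 0.1244 ≈ 1.60.
- Stage 2: 7(0.0334) + 6(0.0459) + 5(0.0469) + 4(0.0423) + 3(0.0356) + 2(0.0286) + 0.0222 ≈ 1.10.
- Total 2.70, so expected enrolment is 10.84 − 2.70 = 8.14.

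Expected treated is p times expected enrolled, so the saving in treated women is 0.60 × 2.70 = 1.62.

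| True p | Enrolled, as written | Enrolled, with stop | Fewer enrolled | Fewer treated | P(at least one enrolled after rejection is certain) |
|---|---|---|---|---|---|
| 0.60 | 10.84 | 8.14 | 2.70 | 1.62 | 83.5% |
| 0.70 | 12.97 | 10.87 | 2.10 | 1.47 | 67% |
| 0.80 | 15.17 | 14.09 | 1.09 | 0.87 | 37.1% |
| 0.90 | 16.66 | 16.47 | 0.19 | 0.17 | 7.0% |

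Differences were taken before rounding.

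**5. Error rates.** Every path cut short would have ended in rejection, so P(accept) is unchanged at every p: 0.0436 at 0.60 and 0.9045 at 0.90.

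**6. The largest savings.** Five women in stage 1 needs three failures in a row: 0.4³ = 6.4% at p = 0.60 and 0.1³ = 0.1% at 0.90. Seven in stage 2 has probability 28 × 0.4⁴ × 0.6⁶ = 3.3% at 0.60 and 28 × 0.1⁴ × 0.9⁶ = 0.15% at 0.90. These are alternatives and cannot both occur in one trial.

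**The case against.** The strongest reply is that nothing is wrong. This is a standard design, its operating characteristics are right, and curtailment is an optional refinement. That stands: a reader might infer a flaw in type I error or power, and there is none. The protocol is also silent on accrual after the boundary is crossed; it does not expressly require it. Its fixed counts nevertheless leave no basis for stopping sooner.

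Second, later patients are not uninformative. The primary objective covers feasibility and safety, section 10.1 makes an estimate of reproducibility a primary feasibility endpoint, and comfort and acute toxicity are secondary endpoints. A reader might infer that women enrolled after the boundary contribute nothing. They cannot reverse the accept/reject count, but they do inform these other endpoints. An early stop costs precision: with 0 of 3 acceptable, the exact 95% interval runs to 1 − 0.025^(1/3) = 71%. This is a real cost, though borne for a device already rejected. It also explains why accrual should continue to 17 once success is secured, where safety data bear on a device that may go forward.

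Third, exposure should be counted in treated women. Women whose plans fail do not receive the boost, and those treated have plans that passed. A reader might take 2.7 as the number needlessly irradiated under the null; about 1.6 is the right figure. Nor is the device untested: section 11 reports extensive phantom work, and the cup was studied beforehand. First-in-human is the accurate description.

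Fourth, a stop triggered by one plan needs an unambiguous grade, which the protocol does not yet give. This stands and is taken up in the fix.

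**Conclusion.** The point holds as a cheap improvement to a correctly computed design. As written, the trial can go on enrolling after its decision is fixed, with probability 83.5% at true acceptability 60%, 37% at 80% and 7% at 90%. Stopping at the decisive plan changes neither error rate. The gain is concentrated where the device underperforms and is close to nil if it performs as hoped: about 0.2 women enrolled or treated at 90%.

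A reader might add the two largest savings into a worst case of 12 women. The documents do not support that, since one requires the trial to end in stage 1 and the other requires it to continue.

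The figures assume independent plans with a common probability of acceptability, that each plan is graded before the next woman is enrolled, and that every woman with an acceptable plan is treated. If registrations overlap, the saving in enrolment is smaller.

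**What to change.** Add to section 10.2: *Accrual stops for futility at the third unacceptable plan among the first 8 patients, or at the fourth unacceptable plan overall; otherwise accrual continues to 17.* Restate the expected sample size under the null as 8.1. The 4.4% and 90.5% stay. The 68% also stays, as the probability of stopping by the end of stage 1.

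Because the stop depends on the count, the same edit should:
- reconcile the scoring reference: section 10.1 points to 5.4.3, while section 10.2 points to 5.5.4, which holds whole-breast criteria;
- state whether a minor deviation counts as acceptable;
- reconcile the minimum PTV dose for an acceptable plan, given as 7.2 Gy in section 1.3 and 7.6 Gy in section 5.4.3;
- say whether women who never reach a graded plan (a clip above the cup rim, seal loss, discomfort) count among the 8 or 17.

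The stopping rule itself is one sentence; the grading definitions need a little more work but are required for the present rule too. The scientific cost is fewer comfort and acute toxicity records and a less precise reproducibility estimate, only in a trial that has already rejected the device.
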